## 2. Glossary

CI	Chief Investigator
eCRF	Electronic Case Report Form
GCP	Good Clinical Practice
HRA	Health Research Authority
IRAS	Integrated Research Application System
ISF	Investigator Site File
Participant	An individual who takes part in a clinical study
PI	Principal Investigator
QMUL	Queen Mary University of London
REC	Research Ethics Committee
TMF	Trial Master File

#### 4. Summary and Synopsis

Short title	SAPPHIRE study
Methodology	National, multi-centre prospective observational cohort study collecting only anonymised data
Research sites	NHS hospitals undertaking elective surgery as listed above
Objectives	
 
1. To identify association between the use of perioperative antimicrobial drugs and the incidence of postoperative surgical site infection.
 
2. To identify association between the use of perioperative antimicrobial drugs and other perioperative complications.
 
3. To identify association between antimicrobial allergy labels and perioperative complications.
 

Number of participants	13,720 patients data sets
Inclusion criteria	
Adult patients (aged <math>\geq 18</math> years) undergoing one of the following surgical procedures:
 
 
• Primary hip or knee replacement
 
• Internal fixation of a closed long bone fracture (upper or lower limb)
 
• Colorectal resection
 
• Trans-urethral resection of prostate or bladder tumour
 
• Caesarean section
 
• Hysterectomy (vaginal or abdominal)
 

Exclusion criteria	
 
• Use of antibiotics in the two weeks prior to surgery
 
• Previous participation in the study
 

Statistical methodology and analysis	
Continuous variables will be reported as a mean with standard deviation or median with interquartile range. Multivariable regression analysis will be used to test associations between exposure and outcome measures, adjusting for pre-specified covariates that are plausibly associated with both exposure and outcome. Logistic regression models will be used for binary outcomes and linear regression models for continuous outcomes. The threshold for statistical significance will be 5%. A single final analysis is planned at the end of the study.

Study duration	31 months
----------------	-----------

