### **7.5. Secondary outcome measures**

- Number of antimicrobials to treat an infection
- Incidence of antimicrobial side effects within 30 days after surgery:
  - Acute kidney injury of any cause
  - Diarrhoeal illness of any cause

- Hearing loss, tinnitus or vertigo of any cause
- Suspected allergic reaction to antimicrobials
- Suspected allergic reaction to any other drug
- Incidence of postoperative infection within 30 days after surgery
- Incidence of all postoperative complications within 30 days after surgery
- Mortality at 30 days

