### **7.6. Process measures**

- Duration of hospital stay (number of days from surgery until hospital discharge)
- Critical care admission (level two or level three)\*
- Duration of critical care days (level two or level three)\*

\*A full list of definitions is available in the appendix A

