## **9. Statistical Considerations**

We will use a pre-specified statistical analysis plan. The sample size required to detect an association between SSI and dose was calculated using the 'simsam' package in STATA (Version 17.0), which uses simulation. We assumed that dose was a Poisson random variable with mean and variance 2, and that there was a linear relationship between  $\log(p/(1-p))$  and dose, where  $p$  is the risk of SSI. To specify the association we would like power to detect we specified the SSI risk at the mean dose (10%) and the SSI risk at dose 0 (12%), which then determines the coefficients in the linear relationship between  $\log(p/(1-p))$  and dose. To demonstrate an association between dose and SSI risk using logistic regression, with 90% power at the 5% significance level, we require 6000 patients. Also, to demonstrate an association between allergy label (binary exposure) and complications. The incidence of complications in exposed 15% and unexposed 10%, with 80% power at the 5% significance level we require 1372 patients. However, we expect only 10% of the sample to have an allergy label, so the total sample size would need to be 13720. Considering both sample size calculations for our primary and principal secondary outcomes we aim to recruit a total 13720 patients.

The primary analysis will test associations between antimicrobial prophylaxis and surgical site infection. Secondary analyses will examine the association between the type and number of doses of antimicrobial prophylaxis and potential antibiotic-related harms (including allergic reactions, acute kidney injury, diarrhoeal illness within 30 days after surgery), as well as other postoperative infective complications within 30 days after surgery, and mortality at 30 days. In addition, we will examine any associations between the presence of drug allergy labels and SSI, other postoperative infections and antibiotic-related complications. We will report continuous variables as mean with standard deviation or median with interquartile range. We will use multivariable regression analysis to test associations between exposure and outcome measures, adjusting for pre-specified covariates that are plausibly associated with both exposure and outcome. We will use logistic regression models for binary outcomes and linear regression models for continuous outcomes. The threshold for statistical

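### Linear regression is the only model named for non-binary outcomes, but those listed are a count and two durations, so constant-variance intervals can be miscalibrated

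*Protocol*

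**What the plan says.** Two places in the protocol fix the model family. Section 4 (Summary and Synopsis) says "Logistic regression models will be used for binary outcomes and linear regression models for continuous outcomes", and section 9 (Statistical Considerations) says "We will use logistic regression models for binary outcomes and linear regression models for continuous outcomes". Section 9 gives the scope: "We will use multivariable regression analysis to test associations between exposure and outcome measures", with covariate adjustment.

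Sections 7.3 to 7.6 list three measures that are not binary:

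- Section 7.5, a secondary outcome: "Number of antimicrobials to treat an infection". This is a count.
- Section 7.6, a process measure: "Duration of hospital stay (number of days from surgery until hospital discharge". This is a duration in days.
- Section 7.6, a process measure: "Duration of critical care days (level two or level three". This is also a duration, and it is zero for anyone who never received level two or three care.

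For description, section 9 says "We will report continuous variables as mean with standard deviation or median with interquartile range", so skew is foreseen in the summaries. Nothing comparable is said about the models. Section 9 also refers to a separate plan ("We will use a pre-specified statistical analysis plan"), which is not at hand.

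**The concern.** No approximately normal continuous outcome is listed, so the linear-model sentence applies to these three measures or to nothing. For counts and durations a group with a higher mean usually has a higher variance too. The usual linear-model standard error pools one variance over everyone. If the smaller group has the larger variance, that standard error is too small; if it has the smaller variance, it is too large. A bigger sample does not correct this.

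The protocol gives reasons to expect differences. Section 6.1 says that patients with surgical site infection stay longer and links penicillin avoidance to harm. Section 9 assumes complications in 15% of labelled against 10% of unlabelled patients, with only 10% labelled. Section 7.7 pools operations as different as transurethral and colorectal resection. At stake is the calibration of intervals and tests for these three measures only.

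**Working it through.** **Inputs.** From section 9: 10% of patients labelled, 13,720 patients in total, dose assumed Poisson with mean 2. The protocol states no mean, variance or share of zeros for the three measures and no precision figure for them, so there is nothing to reproduce. Everything about their distribution below is an assumption.

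**1. Allergy label, closed form.** Let k be the outcome variance in labelled patients divided by that in unlabelled patients. Up to a common factor, the variance of the difference in means is

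- true: k/0.1 + 1/0.9
- as estimated with one pooled variance: (0.1k + 0.9) × (1/0.1 + 1/0.9)

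With R = √(true/pooled), a nominal 95% interval covers P(|Z| < 1.96/R).

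| k | true | pooled | R | coverage |
|---|---|---|---|---|
| 0.5 | 6.11 | 10.56 | 0.761 | 99% |
| 1 | 11.11 | 11.11 | 1.000 | 95% |
| 1.2 | 13.11 | 11.33 | 1.076 | 93% |
| 1.5 | 16.11 | 11.67 | 1.175 | 90% |
| 2 | 21.11 | 12.22 | 1.314 | 86% |

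At k = 2 the ordinary standard error is 1/1.314 = 0.76 of what it should be, so 24% too small. At k = 0.5 it is 1/0.761 = 1.31 times what it should be, so 31% too large.

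**2. Allergy label, simulation.** 13,720 patients, 2000 runs per scenario. Assumed shapes: stay log-normal (log-scale SD 0.8); critical care days zero or log-normal; count zero or 1 + Poisson(0.8).

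| Measure and scenario | ordinary | robust |
|---|---|---|
| Stay, no difference | 95.0% | 94.6% |
| Stay, mean ratio 1.2 | 92.0% | 95.7% |
| Stay, mean ratio 1.5 | 84.5% | 95.0% |
| Count, 10% v 10% treated | 94.8% | 94.6% |
| Count, 10% v 15% | 90.8% | 94.6% |
| Count, 5% v 10% | 87.4% | 94.4% |
| Critical care days, 5% v 5% admitted | 95.0% | 92.2% |
| Critical care days, 5% v 7.5% | 89.4% | 93.4% |
| Critical care days, 5% v 10% | 86.4% | 93.9% |
| Critical care days, 2% v 4% | 86.8% | 92.2% |

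Where the groups do not differ, ordinary intervals hold their level despite skew and zeros. Robust intervals are close to nominal for stay and the count. For critical care days by label they are a little low, including the no-difference case, where the ordinary interval was right.

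**3. Dose, simulation.** With dose Poisson(2), ordinary coverage was 95.0% for critical care days unrelated to dose, 92.0% for critical care days rising with dose, 85.2% for stay rising with dose at a constant coefficient of variation, and 95.6% for the count when infection risk follows the slope in the protocol's own sample size calculation (12% at dose 0, 10% at dose 2).

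**4. Pooled procedures, no dose effect, procedure-adjusted.** Assume six equal-sized procedures with mean doses 2, 1.5, 4, 1, 1.5, 2 and mean stays 3, 4, 7, 1.5, 2.5, 2 days at a constant coefficient of variation, so that variance is proportional to the squared mean.

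- Average variance: (9 + 16 + 49 + 2.25 + 6.25 + 4)/6 = 14.42.
- Dose-weighted variance, which governs the true error because dose varies more where its mean is higher: (18 + 24 + 196 + 2.25 + 9.375 + 8)/12 = 257.625/12 = 21.47.
- R = √(21.47/14.42) = 1.22, and type I error = P(|Z| > 1.96/1.22) = 10.8%.

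Simulation of this case gave 11.0% for stay, and 12.0% for critical care days with assumed admission risks of 1% to 20% by procedure. With robust standard errors the figures were 5.3% and 4.9%. Other assumed spreads of stay gave 5% to 9%, against about 5% with robust standard errors.

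**The case against.** The best defence is that the statistical analysis plan is not shown, and the choice of variance estimator or count model is ordinary content for it. A reader might therefore infer that a method is missing. The document does not support that, and it is not the point made here. The point concerns what the protocol does fix, twice: one model for non-binary outcomes, which suits the listed ones poorly unless the variance is handled. The defence is right that the sentence does not commit to constant-variance standard errors and never calls the count continuous. Robust errors fit inside the present wording, which is why the repair is small.

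It is also fair that hospital and critical care days are labelled process measures, and that section 9 does not name them, or the antimicrobial count, among its planned analyses. That limits the reach of the point. It does not remove it, because without these three the linear-model sentence has no object.

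Three stronger readings are tempting, and the documents do not support them:

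- *Skew and zeros make linear intervals wrong.* With equal variances coverage is about 95% for all three measures at this sample size. Nor can hospital stay be taken to be mostly zero.
- *The intervals would be too narrow.* Below a variance ratio of 1 they are too wide, and the protocol gives nothing that fixes the ratio.
- *Deaths would count as favourable short stays.* Section 7.6 counts days to discharge and does not say how a death in hospital is coded. The value is undefined, not short.

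**Conclusion.** The point holds in limited form, and its severity is minor. The named model fits the three non-binary measures poorly if it is run with constant-variance standard errors, and the cause is unequal variance. For the allergy label, coverage runs from 99% to 86% over an assumed variance ratio of 0.5 to 2 and is 95% at equality. For dose across pooled procedures, type I error ran from 5% to 12% under the assumed spreads. None of these distributions comes from the protocol, so the figures show what can happen and do not predict what will. The primary outcome, the other secondary outcomes and both sample size calculations concern binary outcomes and are untouched.

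**What to change.** Amend the sentence in sections 4 and 9 so that linear models for the antimicrobial count, hospital days and critical care days use heteroscedasticity-robust standard errors. The mean difference remains the estimand.

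Two supporting analyses may be added: a count model for the number of treatment antimicrobials, and time to discharge alive with in-hospital death as a competing event. They should stay supporting, because they change the estimand to a ratio or a discharge hazard and bring assumptions of their own.

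The cost is one sentence in two places, with no new data and no change to the sample size. Some intervals will be slightly wider. For critical care days by allergy label, robust intervals may still fall a little short (92% to 94% in the simulations), which the report should acknowledge.

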## 6. Introduction

### 6.1. Background

Surgical site infection (SSI) is an important and preventable cause of postoperative morbidity which affects 250,000 of the five million NHS patients who undergo surgery every year. Patients who develop SSIs stay longer in hospital, have an increased mortality, and can experience poorer quality of life. Treatment of SSIs is also associated with significant healthcare costs to healthcare providers.

Antimicrobial prophylaxis is an important method for preventing SSI and is a widely used practice in surgical care. However, advances in surgical techniques (e.g. laparoscopic and robotic), operative theatre design (e.g. laminar flow air conditioning) and perioperative care (e.g. pre-operative patient showers) have reduced the inherent risk of SSI. The evidence supporting the use of antimicrobial prophylaxis has significant limitations, with many trials conducted more than 20 years ago and potentially less relevant to contemporary practice. We conducted an extensive systematic review and meta-analysis and found that while antimicrobial prophylaxis is associated with a 1% absolute risk reduction for SSI, the evidence quality was poor. In a number of surgical groups, patients receiving prolonged course of prophylaxis experienced a small benefit in terms of infection risk, compared to those receiving short-duration courses (Risk Difference -0.01 [-0.02 to -0.01]; I=52%). A similar result was seen when comparing no prophylaxis to ≥1 dose (Risk Difference -0.02 [-0.03 to -0.02]; I=62%). This suggests that antimicrobial prophylaxis might not be required in the doses currently prescribed or, in some cases, not required at all.

The side effects and harms caused by antimicrobial drugs can be substantial, with 1 in 50 surgical patients suffering complications directly attributable to antimicrobial use including acute kidney injury, hearing loss and anaphylaxis. A recent national audit identified antimicrobials as the single commonest cause of life-threatening allergic reactions during surgery. In addition, self-reported antimicrobial allergy can lead to harm from the use of alternative antimicrobial drugs that are less effective and more toxic. Up to 1 in 7 patients carries such a label, although a diagnosis of allergy has rarely been proven through specialist allergy investigation. Previous work has demonstrated that the most common antibiotic allergy is to penicillin, with this label carried by 12% (2624/21,224) of elective surgical patients in the UK. Of such patients, half received second-line antimicrobial drugs and 40% received either no prophylaxis,

or a drug not recommended by local guidelines. Based on these findings, an estimated 100,000 patients every year may be unnecessarily denied penicillin-based antibiotics. Avoidance of penicillin is a recognised cause of harm in a variety of patient groups, associated with increased nosocomial infections, increased wound infections, and higher mortality. Other research has demonstrated increased length of stay for mixed populations of hospital in-patients. The scale of this problem is unknown because there is no system to report antimicrobial use and its associated harms.

At a societal level, the use of antimicrobial drugs is the principal cause of antimicrobial resistance and represents a fundamental threat to our society and to contemporary and future healthcare. One third of hospital in-patients receive antimicrobial drugs but as many as two thirds of these prescriptions may be inappropriate in terms of indication, duration or dose. Antimicrobial prophylaxis represents a major driver of antimicrobial resistance and may increase the number of untreatable surgical infections. Antimicrobial prophylaxis may be associated with a small reduction in the risk of surgical site infection, but the evidence quality is poor. Limited reporting of harm makes it difficult to balance risks and benefits of this widely used intervention. The over-arching aim of our research is to provide contemporary evidence for perioperative antimicrobial prophylaxis and find safe ways to minimise the use of these drugs.

## **6.2. Rationale**

Our aims of the study are to provide detailed data describing the clinical effectiveness of antimicrobial prophylaxis and define the risks of harm during the perioperative period. This will include:

1. An understanding of the treatment effect of antimicrobial prophylaxis in preventing SSI
2. Description of clinically relevant harm associated with the use of antimicrobial prophylaxis
3. Details of any association between drug allergy labels and SSI

## **7. Study Objectives**

### **7.1. Exposures of interest**

- Number of doses of antimicrobial drugs administered as prophylaxis before, during or after surgery to prevent an infection
- Label of allergy to any drug

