### **7.4. Secondary objectives**

To describe any associations between number of doses of antimicrobial prophylaxis or presence of an allergy label and the following:

- Antimicrobial side effects
- Postoperative infections
- Other complications (listed in appendix)
- Mortality at 30 days after surgery

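### The allergy comparison that sets N = 13,720 has conflicting exposure definitions and no designated outcome, and 13,720 does not correspond to its stated 80% power

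*Protocol*

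**What the plan says.** **Exposure.**
- Synopsis (section 4), objective 3: "To identify association between antimicrobial allergy labels and perioperative complications".
- Section 7.1: "Label of allergy to any drug".
- Section 7.4 leaves the type of label open: "presence of an allergy label and the following".
- Section 6.2 and the analysis text of section 9 speak of drug allergy labels without further definition.

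**Outcome.**
- The sample size text in section 9 aims "to demonstrate an association between allergy label (binary exposure) and complications", with complications not defined.
- The analysis text of the same section relates labels to a different set: "the presence of drug allergy labels and SSI, other postoperative infections and antibiotic-related complications".
- Section 7.5 lists "Incidence of all postoperative complications within 30 days after surgery" among several secondary outcomes and ranks none of them.
- Section 9 nevertheless justifies the total by "Considering both sample size calculations for our primary and principal secondary outcomes".

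**Sample size.** Section 9 assumes 15% v 10%, 80% power and a 5% level, and obtains 1,372. It then divides by an expected label prevalence of 10% to reach 13,720. The primary analysis needs 6,000, so the allergy comparison sets N.

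**Prevalence.** For penicillin labels alone, section 6.1 reports "with this label carried by 12% (2624/21,224) of elective surgical patients in the UK". It puts antimicrobial labels at up to 1 in 7.

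**The concern.** A label to any drug and a label to an antimicrobial define different exposed groups. The harm described in section 6.1 works through antimicrobials: a labelled patient receives an alternative agent, or none. A label to an unrelated drug has no such route, and the protocol offers no other rationale for counting it. A result based on the 7.1 definition would therefore answer a different question from objective 3.

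The outcome has a similar problem. The sample size rests on complications, but the allergy analyses described in section 9 do not include overall complications. With more than one exposure and several outcomes in the text, the comparison that adds 13,720 − 6,000 = 7,720 patients beyond the primary requirement could be settled after the data are seen. The stated 80% is then not tied to a defined analysis.

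**Working it through.** All figures are unadjusted two-proportion calculations at a two-sided 5% level (the protocol does not state sidedness), without continuity correction, hospital clustering or covariates. Risks are p1 (labelled) and p0 (unlabelled), n1 is the number labelled, r is the ratio of unlabelled to labelled, and p̄ is the overall risk.

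n1 = [1.96·√(p̄(1−p̄)(1+1/r)) + 0.8416·√(p1(1−p1) + p0(1−p0)/r)]² / (p1−p0)²

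**1. The protocol's figure.** With p1 = 0.15, p0 = 0.10, r = 1 and p̄ = 0.125:
- n1 = [1.96·√0.21875 + 0.8416·√0.2175]² / 0.0025 = (0.9167 + 0.3925)² / 0.0025 = 685.6, so 686 per group and 1,372 in total.
- 1,372 / 0.10 = 13,720.

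Both stated numbers reproduce exactly. They show that 1,372 is the total of two equal groups, which section 9 then treats as the number of labelled patients.

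**2. The same inputs with 10% labelled.** With r = 9 and p̄ = 0.105:
- n1 = [1.96·√0.104417 + 0.8416·√0.1375]² / 0.0025 = (0.6333 + 0.3121)² / 0.0025 = 357.5, so 358 labelled and 3,580 in total. For 90% power: 492 labelled and 4,920 in total.
- Power at 13,720 (1,372 v 12,348): z = (0.05·√1372 − 0.6333) / √0.1375 = (1.8520 − 0.6333) / 0.3708 = 3.29, so 99.9%.

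**3. Prevalence.** The planned 10% is below section 6.1's 12% for penicillin labels alone. In the same population, an any-drug label cannot be rarer than its penicillin subset. At 12% or 1 in 7 labelled, the 80% requirement for 15% v 10% falls to about 3,058 or 2,653.

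**4. What the any-drug definition could do.** The protocol gives neither the any-drug prevalence q nor the risk with other labels. Assume that antimicrobial labels (prevalence a) carry 15% risk, and that other labels carry the unlabelled 10%. The labelled group's risk is then p1 = 0.10 + 0.05·a/q. At N = 13,720:

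| q (assumed) | p1 at a = 12% | Power, a = 10% | Power, a = 12% | Power, a = 1 in 7 |
|---|---|---|---|---|
| 20% | 13.0% | 96.1% | 99.3% | 99.9% |
| 25% | 12.4% | 90.3% | 97.2% | 99.5% |
| 30% | 12.0% | 82.5% | 93.1% | 98.2% |
| 40% | 11.5% | 64.7% | 79.6% | 90.9% |

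The 12% is the penicillin figure used as a stand-in for antimicrobial labels. At that value, a 5-point difference becomes 3 to 2 points for q of 20% to 30%, yet power stays at 93% or more. The larger labelled group and the oversized N absorb the loss.

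**5. Outcome.** Setting sections 7.5 and 9 side by side, the all-complications item in 7.5 is the natural match for the sample size. No sentence makes that link, and section 9's allergy analyses leave it out.

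**The case against.** The strongest reply is that this is loose wording with an obvious reading. Sections 6.2, 7.1 and 9 all refer to drug labels, so the synopsis could be the outlier. Section 7.5 also lists suspected allergic reactions to drugs other than antimicrobials, for which other labels are relevant. The all-complications outcome is listed, even if unranked. SSI is among the allergy analyses, and section 9 puts its risk at 10% at the mean number of prophylactic doses. A 15% v 10% contrast on SSI would therefore have the same power. The statistical analysis plan may settle the rest.

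Much of this stands. The outcome is unidentified rather than absent, and the investigators may legitimately choose either exposure. What does not go away is that the protocol's own statements conflict on the comparison that sets N.

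Three stronger readings are not supported:
- A reader might infer that the any-drug definition dilutes the effect and leaves the study underpowered. Attenuation is conditional on a risk the protocol does not give, and does not arise if the antimicrobial label is analysed. Under the assumptions above, power falls below 80% only at high any-drug prevalence.
- A reader might take section 6.1's 1 in 50 as the baseline for antibiotic-related harms and conclude that those analyses are underpowered. That figure counts complications directly attributable to antimicrobials. Section 7.5 counts events such as kidney injury and diarrhoea of any cause, which is broader, and the protocol states no effect size for them.
- A reader might infer that recruitment should fall to 6,000, since 3,580 is below it. The calculations ignore adjustment and clustering, and the outcome is not yet fixed.

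**Conclusion.** The concern holds as an inconsistency in the comparison that determines the sample size. The exposure differs between synopsis objective 3 and section 7.1. The powered outcome is not identified in 7.5 and does not appear among section 9's allergy analyses. If 7.1 is followed, the estimate does not answer objective 3, and is pulled towards the null if other labels carry no excess risk.

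The damage is to interpretation, not necessarily to power. The step from 1,372 to 13,720 uses a two-group total as the number labelled, so N is about 3.8 times what the stated inputs require (13,720 / 3,580). The contradictions and the arithmetic rest on the protocol alone, apart from the assumption of a two-sided test. The attenuation figures rest on assumed prevalences and on an assumed absence of excess risk with other labels. This should be corrected, but it does not threaten the primary analysis.

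**What to change.** - **Exposure.** Use one label definition for the principal allergy comparison in the synopsis and sections 7.1, 7.4 and 9. The antimicrobial label matches objective 3 and the rationale in 6.1, with labels to other drugs kept as a separate category. If any-drug labels are intended, change the synopsis instead.
- **Outcome.** In 7.5, name the all-complications outcome within 30 days as the principal secondary outcome, and add it to the allergy analyses in section 9.
- **Power.** Restate it with unequal groups and a prevalence that fits the chosen definition, and say what 13,720 provides.

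Whether to adjust the allergy model for drug type and number of doses can be left to the statistical analysis plan. The cost is a few sentences and one recalculation. No new data are needed if the record shows which drug each label refers to.
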